### ***Eligibility criteria***

Inclusion criteria for invitation are:

- Previously given informed consent to participate in the FH-Risk study at the Nightingale Centre.
- Consented to and have received their re-evaluated risk at a clinic appointment (see Part 1).
- Consented to be contacted about future research.

- Who are still in follow-up at the FHRPC.
- Aged between 25 and 60.
- Have not developed breast cancer.
- Able to consent to participate in a research study.

Exclusion criteria are:

- Women who have received a diagnosis of breast cancer.
- Women who lack the capacity to consent.

### **Part 3 Study Procedure**

Only women who consent to having a clinical appointment to discuss their re-evaluated risk estimate and consented to take part in future research will be invited to this interview study. The interview study will be mentioned to the women at the end of their clinical appointment to assess their interest in taking part. As mentioned above women will complete an expression of interest and consent to contact form and a consent form prior to their clinical appointment. On these forms there is a statement which asks if the participant is happy for the research team to retain her contact details in order to invite her to related future research and whether their contact details ONLY can be passed a member of the research team based at UoM. Therefore information about this study will only be sent to women who consent to this statement. Reminder invite letters will be sent out if deemed necessary (based on participant numbers).

#### **Inviting women to interview**

Inviting women to interview in Part 3 will follow the same format as Part 2.

#### **Setting**

The same settings for part 2 apply for part 3.

#### **Materials and Methods**

Telephone and Zoom interviewing will be given as the only option during COVID-19 restrictions. Should restrictions change and allow for face to face interviewing, women can choose to be interviewed at the University of Manchester, their homes or a private location of their choosing. The participant information sheet has been created with additional information in relation to in person interviewing and Covid-19.

Audio recorded consent will be taken at the beginning of each interview. The researcher will read out the statements and ask whether the interviewee agrees. This will be recorded on an encrypted device separately from the study data. If interviews are able to take place in person the participant will be required to read and sign a physical copy of the consent form. With consent, interviews will be audio-

recorded using an encrypted device. The researcher may take notes during the interview and this will be used as field notes only and will be destroyed at the end of the study data analysis. When zoom is used we will not video record the session. Instead the audio recorder will be placed next to the computer speaker. This has worked for colleagues and reduces the amount of identifiable data produce by the study.

Women taking part in these interviews will be asked to read aloud the materials that are applicable to their risk status, i.e. risk has gone up, risk has stayed the same and risk has gone down. Materials could include letters and information leaflets. As interviews may take place over the telephone the researchers will post or email the materials to the participant prior to the interview taking place. If interviews take place over Zoom the researcher will either post or email the materials or share their screen with the participant so they are able to read the materials. Interviews will be approximately 60 minutes in length.

Following these interviews we will refine the materials based on the appraisals the women have provided. Once refined we will present the materials to a PPIE panel to request their feedback. Materials will be refined again following any PPIE feedback.

A topic guide will be used for the semi-structured component of the interviews and will be piloted before use. At the point of consent we will ask participants to provide some non-mandatory demographical information; which will be used to describe the sample when the findings are written up. Consent to use each participant's postcode to calculate an Index of Multiple Deprivation (IMD) will also be requested to use as a measure of deprivation when describing the study sample during write-up. Once the deprivation score has been obtained the postcode will be destroyed.

With consent, medical data will be accessed after the interview including women's initial risk and re-evaluated risk estimates held within medical records at MFT (women will consent for the research team to access their medical records as indicated on the study consent form). Relevant medical data (for example, chemoprevention uptake, and frequency of mammogram attendance) will be extracted using a case report form (CRF). The CRF will be filled in by the consultant and will be provided to the researcher electronically without any personal identifiable data present. This will be provided as full data set for all the participants.

## Analysis

A content analysis will be performed on the 'think aloud' data between each round of interviews. The conventional form of content analysis will be used where researchers explore the number of commonalities in the data. Thus, content analysis enables the researcher to systematically describe

the data by extracting the amount of times a point is raised by participants (Hsieh & Shannon 2005). Analysing in this way will allow the researcher to identify the commonalities and consistencies in participants' comments in order to refine materials in line with these views (Hsieh & Shannon 2005). For the brief semi-structured section of the interviews a manifest, inductive thematic analysis will be used as described in study 1. Findings from these interviews will be used to inform changes to information materials.

### **3.6 Data management for Part 2 and 3 (qualitative interviews)**

We are collecting and storing data in accordance with the General Data Protection Regulation (GDPR) and Data Protection Act 2018 which legislate to protect participants' personal information.

The clinical care team/authorised members of the research team in Part 1 of this study will provide the UoM researcher with the contact details of women who indicated that they would be happy for their details to be shared with the UoM researcher in order for them to contact her about future related and ethically approved research. Their consent to be contacted will be recorded on the expression of interest and consent to contact form issued in Part 1. The clinical care team/authorised members of the research team in Part 1 will either enter women's details into an excel file and send the file password protected via secure email or will telephone the UoM researcher who will input the details into a password protected excel file stored on the University's Research Storage Service (Isilon). Each participant taking part in Part 2 and 3 of this study will be provided with a reference code used to label which interview they took part in. Participants will also be given pseudonyms in place of their real names in transcripts and publications. A password protected file containing the reference codes and pseudonyms for each participant will be kept on the University's secure server (p:drive) stored separately from study data. Study data (audio recordings and anonymised transcripts) will be kept on the University's Research Storage Service (Isilon). Audio recordings will be stored separately from other study data. Excel files containing participants' identifiable information will also be stored on Isilon. All files will be password protected. Only authorised members of the research team will be able to link this data together should participants want to withdraw their contribution. Files containing reference codes and pseudonyms will be deleted after a participants data has become part of the wider dataset, approximately 2 weeks after the interview. Contact details will only be retained if women consent to being contacted about future research. These details will be retained for up to 10 years after the study has ended. If and when women are contacted about future research they will be given the option to have their details deleted from the database. For those who do not consent for their details to be retained, their details will be deleted after results have been written up for publication and participants who requested it have received a summary of the results. After this point

the research team will not be able to identify participants from the data. Only authorised members of the research team will have access to this data. This data will be kept strictly confidential.

Forms containing demographical information will be added to a excel spreadsheet. Paper copies will be shredded by the University's service for disposing of sensitive documents. This excel file will be password protected and stored on Isilon and will be destroyed when findings have been written up for publication. With consent, medical data will be accessed after the interview including women's initial risk and re-evaluated risk estimates held within medical records at MFT (women will consent for the research team to access their medical records as indicated on the study consent form). Relevant medical data (for example, chemoprevention uptake, and frequency of mammogram attendance) will be extracted using a case report form (CRF). The CRF will be filled in by the consultant in part 1 and will be provided to the researcher electronically without any personal identifiable data present. This information will be added to the demographic information excel file. This excel file will be password protected and stored on Isilon and will be destroyed when findings have been written up for publication.

Audio recordings of all interviews will be recorded on an encrypted audio device. Video footage from zoom will not be recorded. Interviews will take place in a private location and where possible identifiable information which could be captured on the recording will be avoided. Any identifiable data captured will be replaced during transcription. Once an interview is complete the researcher will store the device securely until uploading to the University's secure server can be carried out (as soon as is feasible). The audio recording will then be uploaded to the University's Research Storage server, password protected and encrypted. The researcher will listen to the recording to check the upload and will then permanently delete the recording off the device. Transcription is to take place via a 3rd party service, approved by the University. Audio files will be uploaded via a secure file upload. Audio files will be stored separately from other study data on the Research Storage server until the final analysis of the results have taken place. After this point audio files will be permanently destroyed. Anonymised transcripts will be stored for up to 10 years following publication. The production and storage of audio files and transcripts will be carried out in accordance with the University's Standard Operating Procedure for secure handling of recordings and transcriptions. All audio recordings including audio recorded consent will be stored separately from other study data.

Should participants wish not to be recorded but would still like to be interviewed the researcher will take notes. These will be typed up, password protected and stored on Isilon. Quotes from these notes will not be used. Original hand written notes will be shredded via the University's shredding of confidential documents service

Recorded consent taken over the telephone/zoom will be stored securely, electronically and separate from the study data. These will be destroyed as per the policy for physical consent forms (for low risk studies: 2 years after the study has been completed) which is in line with University policy. Physical consent forms will be stored in a locked cabinet in the lead researchers locked office at the University for up to 2 years after the study has been completed. Consent forms will then be destroyed.

Anonymised quotes will be used in research conferences, presentations and publications. Pseudonyms will be used with each quote used. Anonymised transcripts may be shared with reputable researchers and organisations (NHS and healthcare organisations) who are required to handle data in the same way as the University. These organisations will have to request to see this anonymised data via a data sharing agreement. No personal information will be shared and participants will not be able to be identified.

In Parts 2 and 3, for the safety of the research staff, members of the study team who will be conducting the interviews will be required to fill out a lone working form detailing the address of the participant should they be interviewed at home. Only authorised members of the research team will have access to this information if needed. These forms will be destroyed when they are no longer required.

#### **Managing distress and disclosure of bad practice:**

We do not anticipate that the content of these interviews will cause any undue discomfort to participants. However, the discussion of a family history of breast cancer could potentially be distressing, as well as any changes to risk. We will follow the University's managing distress policy should participants become distressed or uncomfortable. In the unlikely event of a disclosure of malpractice or gross misconduct, the researcher may be obliged to report such a disclosure, breaking confidentiality.

### **3.7 Part 4: Communicating an updated breast cancer risk: A questionnaire study**

#### **Questionnaire rationale and objectives**

It is well documented in the literature that women either under or over-estimate their risk of developing breast cancer even after the provision of a clinically-derived risk estimate. It is unknown however what women understand about their risk and how they describe their risk following an update which incorporates new strong independent risk factors.

In this questionnaire study we want to examine the relationship between objective risk (i.e. the updated clinical estimate) and women's subjective understanding of their risk following the provision of an updated clinically-derived breast cancer risk estimate. With this we also want to examine women's breast cancer risk knowledge, including whether they perceived a change to their risk and cancer worry.

Specific objectives include:

- To examine whether there is a difference between objective and subjective risk, looking at first risk given in the first FH-Risk study, updated risk (provided in Part 1 of this study) and women's perceived risk.
- To examine the predictors of subjective risk, including objective risk factors such as family history, PRS, breast density and weight.
- To examine whether women have perceived a change to their risk.
- To examine women's breast cancer risk knowledge, including factors which have contributed to their risk.

### **Participants and recruitment**

Women who opted to have their updated breast cancer risk and attended a consultation in Part 1 will be approached for this part of the study. All these women will be eligible apart from those who took part in interviews in Part 2 and 3 and those who did not consent to hearing about future related studies. Approximately 330-350 women will be eligible from Part 1. Women will be invited to take part in this follow-on questionnaire study via post. They will receive an invite letter, PIS, consent form and paper questionnaire, together with a pre-paid returning envelope.

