	
 
• women who have received a breast cancer risk estimate that has not changed category since their initial estimate
 
• women who have received a decreased (by at least one category) breast cancer risk estimate since their initial estimate.
 
 
Part 4 (questionnaire study):
 
Between 300 and 400 questionnaires sent to women who:
 
 
• have had a consultation about their updated breast cancer risk from Part 1 of this study.
 

Study Period	3 years
Research Aims	
 
i) To determine change in NICE categories of risk (average, moderate and high risk) when new risk factors are added to standard breast cancer risk models.
 
ii) To explore how much new risk models (including MD, SNP313 and mutation testing) change risk estimates previously communicated to women as part of the FH-Risk study.
 
iii) To explore whether a change in breast cancer risk affects credibility of how risk is calculated and communicated to women, including trust in its use
 
iv) To use the findings to understand how and in what format(s) changes to breast cancer risk estimates should be communicated in the future to enable women to properly understand change in risk, potential change in management and manage emotional sequelae
 
v) To use the findings to create information materials to communicate changes in breast cancer risk and assess their usability
 
vi) To use the findings to develop a questionnaire to be given to women who previously took part in the FH-Risk study and assess the impact of changed risk in a definitive study
 

Funders & contact details	
NIHR Manchester Biomedical Research Centre Cancer Prevention and Early Detection Theme; [name], University of Manchester, Manchester Cancer Research Centre, [name] Email address: [contact] [contact]
 
This study has been funded by an MRC PhD studentship, awarded to [name] – MR/N013751/1

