#### *Eligibility criteria*

Inclusion criteria for invitation are:

- Previously given informed consent to participate in the FH-Risk study at the Nightingale Centre.
- Consented to/have received their re-evaluated risk at a clinic appointment (see Part 1).
- Consented to be contacted about future research (namely interviews in Part 2 and 3).
- Aged between 25 and 60.
- Have not developed breast cancer.
- Able to consent to participate in a research study.

Exclusion criteria are:

- Women who have received a diagnosis of breast cancer
- Women who lack capacity to consent.

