### Materials and methods

An invite letter, PIS, consent form and paper questionnaire (and pre-paid envelope) have been developed to distribute to women from Part 1 who attended a consultation and consented to hearing about future related research. Data will be gathered by a short questionnaire. Data from women's involvement in Part 1 and the FH-Risk studies will also be gathered from those who consented for their data to be used in future related research.

The questionnaire will include the following measures:

- A measure of comparative risk using the measure proposed by Weinstein (1999; *What does it mean to understand a risk? Evaluating risk comprehension*. *J Natl Cancer I Monogr* 1999; 25: 15-20).
- A measure of absolute risk using lifetime risk thresholds for breast cancer as defined by NICE clinical guidelines.
- A measure developed by the research team assessing for a perceived change in breast cancer risk.
- A measure developed by the research team assessing for women's knowledge about breast cancer risk factors.
- A measure of satisfaction regarding receiving an updated breast cancer risk estimate proposed by French et al (2004; *The psychological costs of inadequate cervical smear test results*. *Br J Cancer*. 2004;91:1887–1892).
- One item from the Leman cancer worry scale (1991) about developing breast cancer (*Psychological side effects of breast cancer screening*. *Health psychology*, 10(4), 259).
- *A free text response option to allow participants to identify anything important to them that the questionnaire may not have asked.*

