## Analysis

Data will be analysed using correlational analysis and regression modelling. For example, correlational analysis will be used to assess the relationship between objective risk and women's subjective understanding of their risk, as well as the correlation between objective and subjective risk and cancer worry. Regression modelling will be used to explore which risk factors women attribute to their risk. Descriptive statistics will also be used for the satisfaction measure.

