Completed paper questionnaires will be securely destroyed once data has been inputted electronically. This data will be pseudonymised using the participant ID number assigned to women when they received their updated breast cancer risk estimate in Part 1. This participant ID is only known to authorised members of the research team. This ID number will be inserted on each questionnaire before dispatch. Once data from their involvement in the present questionnaire study has been added to the data from the FH-Risk studies women's participant ID will be deleted from this database and the dataset anonymised, meaning we will not be able to identify any woman from this data. This will happen approximately 2 weeks after receiving the completed questionnaire.

Electronic material including, the pseudonymised and eventual anonymised database with the FH-Risk study data and questionnaire responses will be stored at the University of Manchester and as well as at Manchester University NHS Foundation Trust (Nightingale Centre, Wythenshawe Hospital) on secure, password protected computers. Electronic files containing 'personal identifiable information' will be deleted when they are no longer needed. Files containing 'personal identifiable information' will not be linked to women's questionnaire data.

The study team at The University of Manchester will have access to personal information and they will anonymise this as soon as possible. Names and any other identifying information will be removed and replaced with the ID number assigned to women in Part 1. The research team will have access to the key that links this ID number to women's personal information. Should women wish to opt out of us retaining this information, they can email the research team to request their removal.

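### Part 4's eligibility rule omits the no-breast-cancer criterion used in Parts 1, 2 and 3, so a woman diagnosed after her Part 1 consultation can be mailed, reminded and analysed

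*Combined protocol and SAP*

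**What the plan says.** The eligibility lists for the Part 1 consultation (Section 3.2), the Part 2 interviews (3.4) and the Part 3 think-aloud interviews (3.5) each require that the woman has not developed breast cancer. Each also excludes "Women who have received a diagnosis of breast cancer".

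Part 4 (Section 3.7) has no such list. Its rule is one sentence: "All these women will be eligible apart from those who took part in interviews in Part 2 and 3". That sentence names one further exception, for women who declined contact about later research. The Study Summary likewise defines the Part 4 sample only as women who "have had a consultation about their updated breast cancer risk from Part 1 of this study".

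The questionnaire (3.7, Materials and methods) includes "A measure of absolute risk using lifetime risk thresholds for breast cancer as defined by NICE clinical guidelines" and "One item from the Leman cancer worry scale (1991) about developing breast cancer". The Analysis paragraph plans correlations of objective with subjective risk, and the "correlation between objective and subjective risk and cancer worry". It states no exclusions.

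On logistics, Section 3.7 (Procedure) plans a reminder about two weeks after the first invitation. The hospital clinical team links replies to Part 1 data, and the ID is removed about two weeks after the questionnaire is received. Section 3.8 says of the Part 1 ID: "This ID number will be inserted on each questionnaire before dispatch". The Procedure also shows that questionnaires have already begun to go out.

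**The concern.** Cancer status can change between the Part 1 consultation and the Part 4 mailing. Parts 2 and 3 recruit only women who had already met the Part 1 criterion, yet both state it again. The protocol therefore treats cancer status as something to apply afresh at each later contact. Part 4 alone leaves it out, and gives no reason.

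Two things are at stake. The first is the participant: a woman with a recent diagnosis may receive a posted pack, and then a reminder, asking how likely she thinks she is to get breast cancer and how much she worries about it. The distress provision in Section 3.6 is written for the interviews, and Sections 3.7 and 3.8 have no counterpart. The second is the analysis: her answers about developing a disease she already has do not measure what the items are meant to measure, yet nothing keeps them out of the correlations.

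**Working it through.** **1. Is the criterion supplied elsewhere?**

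| Place | No-breast-cancer criterion |
|---|---|
| 3.2, Part 1 consultation | Yes |
| 3.4, Part 2 | Yes, restated |
| 3.5, Part 3 | Yes, restated |
| Study Summary, Part 4 entry | No |
| 3.7, all Part 4 paragraphs | No |
| 3.8, Part 4 data management | No |
| 4.0, Consent | No |

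The Part 4 rule is closed (all women, apart from two named groups), so the criterion cannot be read in by implication. The one dated update of incidence data, in Section 3.1, runs to December 2020 and cannot serve as a check for later mailings.

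**2. The plan's own sample size.** Inputs from Section 3.7: r = 0.2, 80% power, alpha 0.05, 330 to 350 eligible, 60% response. By the two-sided Fisher z method:

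n = ((1.960 + 0.842) / atanh(0.2))² + 3 = 193.97, so 194.

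This matches the plan. Expected replies are 350 × 0.60 = 210, also as stated, and 330 × 0.60 = 198 at the lower figure.

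**3. How many women could be affected?** The documents give neither the incidence after consultation nor the interval to mailing. Assumptions: 0.3% to 0.8% a year, and 1 to 3 years (the study period is 3 years).

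- Low: 350 × 0.003 × 1 = 1.05, about 1 woman
- High: 350 × 0.008 × 3 = 8.4, about 8 women
- Expected repliers at 60%: 0.6 to 5.0

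A wider assumption of 0.5% to 1.5% a year over 0.5 to 3 years, using 350 × (1 − exp(−rate × years)), gives 0.9 to 15.4 women.

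**4. Does restoring the exclusion cost the sample size?** At 60% response, 194 replies need 194 / 0.60 = 323.3 women mailed.

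- From 350, up to 26 women can be removed. Removing 8.4 leaves 341.6 × 0.60 = 205 replies, with power about 82%. Removing 15.4 leaves 201, with power 81.4%.
- From 330, up to 6 can be removed. Removing 330 × 0.008 × 3 = 7.9 leaves 193 replies, with power just under 80%. The wider assumption removes up to 14.5 and leaves 189, with power 79.0%.

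**The case against.** The strongest reply has four parts.

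- **Mailing has begun.** Section 3.7 (Procedure) says so. A check before dispatch comes too late for women already mailed, and once IDs are removed a reply can no longer be traced. This stands, and it shapes the fix. The documents do not say how many women remain to be mailed or linked.
- **The counts are assumptions.** This also stands. With a six-month gap and the lower incidence, the expected number is 350 × 0.003 × 0.5 = 0.5 women. The interval, though unstated, is limited by the three-year study period and the expected end of recruitment on 1 June 2024 (Section 5.0, End of study).
- **Staff may screen informally, or the invitation may tell diagnosed women not to reply.** Possible, but the protocol does not say so, and the invitation and information sheet are not among the documents available. Taking part is voluntary and needs signed consent. That limits what is analysed, but does not prevent the pack from arriving.
- **Objective risk is defined in Section 3.7 as the updated clinical estimate.** On that definition, the figure the woman was given remains the planned comparator after a diagnosis. This is fair for the objective measure. It does not rescue the perceived-risk and worry items, which ask about a future event that has already occurred.

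A reader might go further and infer that affected women form discordant pairs at the high end of risk and so distort the correlation in a known direction. The documents do not support that. A diagnosed woman with a high estimate who reports high risk or worry is a concordant pair and would raise the correlation; other answers would lower it. Nothing in the documents shows where on the risk scale these women would fall. A reader might also infer that women who have had risk-reducing surgery were meant to be excluded. Parts 1 to 3 contain no such exclusion, so none has been dropped.

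**Conclusion.** The omission is real, and no other section repairs it. Followed as written, Part 4 admits a woman diagnosed with breast cancer after her consultation, and her reply is analysed. The likely number is small, about 1 to 8 of 350 mailed, and rests wholly on the assumed incidence and interval. The stated sample size is not wrong. Any effect on the correlations is probably small and its direction unknown, so the case for change rests mainly on avoidable distress and secondly on replies that cannot be interpreted. It should be changed because the remedy is specific and cheap. The documents do not show that any diagnosed woman has in fact been mailed.

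**What to change.** Add to Section 3.7 (Participants and recruitment) the breast cancer exclusion already used in Parts 1 to 3, applied at the date of mailing.

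- **Women not yet mailed or reminded:** the hospital team, which can link IDs to patients, checks diagnosis and vital status when the ID is put on the questionnaire, and again before the reminder.
- **Questionnaires already sent:** the clinical team checks diagnosis status at linkage, before the ID is removed about two weeks after receipt. Women diagnosed before they completed the questionnaire are left out of the risk and worry correlations. State this rule in the Analysis paragraph.
- **Replies whose ID has already been removed:** these cannot be checked. Report how many there are as a limitation.

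The cost is a short amendment, a records check, and a few fewer mailings or analysed replies. From 350 mailed at 60% response, 194 is still met. If only 330 are eligible, removing 7 or more would put expected replies slightly below 194, with power between about 79% and 80% over the ranges considered.
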